Multiple chronic conditions (MCCs) are not simply aggregates of several individual conditions. They represent overlapping conditions that often have common root causes, and when grouped together can severely impact treatment options and quality of life for the patient. Primary care providers (PCPs) face many challenges in treating patients with MCCs. They need to help patients be motivated and informed enough to effectively manage their own conditions, but must balance that with the time demands of their practice.¹⁻⁵

MCCs are common and expensive among patients aged ≥ 65 and are associated with lower quality of life, poorer response to treatment, worse medical and psychiatric outcomes, higher mortality, and higher costs of care.⁷ Treatment of MCCs focuses on medical care, but patient self-management and loneliness matter too. Numerous studies indicate that chronic conditions contribute to loneliness and loneliness in turn contributes to reduced functionality and chronic illness.¹¹⁻¹³

The primary purpose of this study is to conduct a randomized clinical trial (RCT) to examine the effects of C-CHESS--a web-based intervention--on health outcomes and healthcare use among older adults with 3 or all of the following 5 common, high-risk chronic conditions: hypertension, hyperlipidemia, diabetes, osteoarthritis and BMI of 30+. Patients in the experimental group will receive treatment as usual (TAU) plus C-CHESS. Patients in the comparison group will receive TAU+internet and links to helpful websites (e.g., NIH SeniorHealth). We assume that about half of participants will have their own computers and Internet access; we will give touchscreen laptops and provide Internet access to those who do not. The RCT will be conducted in primary care clinics that are part of the University of Wisconsin Department of Family Medicine's primary care network and the Medical University of South Carolina's Primary Care Clinics. The study will involve 330 patients age ≥ 65 who will be tracked for a total of 18 months--12 with access to the interventions and 6 months for follow up, with data collected every 6 months.

The C-CHESS Intervention

For the patient, C-CHESS (or ElderTree, as it will be known to participants) provides tools, motivation, and social support to help them manage their specific set of chronic conditions and communicate with peers and their PCP.

For the clinic, C-CHESS has a Clinician Report (CR), a visual dashboard of health-tracking data that can be customized based on the needs of the clinic. The CR provides alerts to the clinician when a patient passes a certain threshold. The dashboard is intended to help clinicians prepare for patient office visits.

BACKGROUND & SIGNIFICANCE

MCCs are common and expensive among patients aged ≥ 65 . Among Medicare beneficiaries, 65% have 3 or more MCCs⁸ and 23% have 5 or more MCCs. People with MCCs account for 90% of Medicare spending.⁹ Per-capita Medicare expenditures increased with the number of chronic conditions from \$211/year for beneficiaries with no chronic conditions to \$13,973/year for those with 4 or more.⁸ Among Medicare beneficiaries in 2010, hypertension (high blood pressure) and hyperlipidemia (high cholesterol) were the 2 most common chronic conditions, affecting 58% and 45% respectively; diabetes affected 28% and arthritis 29%.²²

Treatment of MCCs focuses on medical care, not patient self-management. Most PCPs focus on managing medication and lab results for MCCs and less on strategies and skills for self-management.¹⁰ However, treatment adherence, health tracking, and feedback to clinicians are important for patients with MCCs, given the challenges of polypharmacy and multiple ongoing treatment needs. Additionally, patients need education about how to live with their conditions, given that they are chronic.

The principles of self-management and support are well documented and relate to an array of health behaviors.¹⁴⁻¹⁷ C-CHESS focuses on improving 1) patients' self-management, 2) patients' social

engagement and support, and 3) clinicians' case management (we use *clinician* to refer to physicians, nurse practitioners, and physician assistants).

Studies show that information and communication technologies can improve self-management and healthcare effectiveness. Recent reviews^{18,19} found positive outcomes in 29 of 32 studies of chronic condition interventions delivered via computer and cellphone, with more impact coming from multi-service programs.²⁰ Our intervention will offer an array of services that can be tailored to each patient's multiple needs and is designed to increase the efficiency and effectiveness of clinic-patient interactions.

The Center for Health Enhancement Systems Studies (CHESS). CHESS is a research center at the University of Wisconsin–Madison. Over the past 30 years, CHESS has acquired an international reputation for developing and applying innovative applications of systems engineering principles and communication sciences to healthcare, specifically in interactive healthcare technology for patients, their family members, and providers. We have extensively studied what it takes to successfully implement these technologies within an organization. CHESS research projects are grounded in the belief that technology has the potential to transform and improve individual lives as well as the healthcare field.

CHESS researchers and programmers work with patients, family members, and clinicians to create web and smartphone applications that help individuals cope with health crises or medical concerns. To date, CHESS has created systems for a variety of health conditions, such as breast, colon, and lung cancer; asthma; aging; and addiction.

CHESS has a suite of evolving eHealth web and smartphone based innovations built on the principles of continuing care and self-management: long duration²⁶; assertive outreach²⁷; tracking²⁸; prompts²⁹; action planning³⁰; problem solving¹⁰; self-tailoring¹⁰; peer, family, and care coordination.³³ In randomized clinical trials, previous CHESS innovations significantly improved: 1) asthma control for young children (mediated by relatedness)¹⁸; 2) quality of life and cost of care in HIV patients³⁵; 3) quality of life and self-efficacy in breast cancer patients, including elderly women³⁶; 4) risky drinking³⁹; and 5) symptom distress and length of survival in lung cancer patients (mediated by competence).⁶⁷

Preliminary data

Most clinical trials of CHESS applications have examined its impact on a single chronic condition. One current study, Elder Tree CHESS, targets outcomes and a population similar to those in this study. Elder Tree CHESS is a web site that was developed as part of an AHRQ Center of Excellence in Active Aging grant to help adults 65 and older remain independent, primarily by reducing loneliness. C-CHESS will have as its base the services and design of Elder Tree, but will add new user features and information related to the target chronic conditions as well as a Clinician Report for medical staff.

Elder Tree was tested in an RCT involving 399 older adults from 3 Wisconsin counties (urban, rural, and suburban). We followed participants for 18 months and assessed outcomes at 0, 6, 12, and 18 months.⁴¹

Elder Tree subjects were asked to identify their chronic conditions so we could examine data about the impact of Elder Tree on those with MCCs. We identified 66 older adults with at least 3 of the 4 target MCCs. Subjects' conditions included (in addition to hypertension, hyperlipidemia, diabetes, and arthritis) cancer, pain, depression, anxiety, heart disease, obesity, osteoporosis, and falls. The Elder Tree RCT included 4 measures we plan to use in this study: health-related quality of life, use of primary care services, relatedness (feeling connected with others), and number of symptoms. For the clusters we propose to study in this project, we found moderate (0.4+) to large effect sizes, all favoring Elder Tree, with 2 exceptions in which small effects favored Elder Tree. These data helped us conduct power analyses and estimate sample sizes for the C-CHESS RCT.

Effect sizes from Elder Tree data					
Chronic Condition Clusters	n Control/ Elder Tree	Quality of Life	Fewer Primary Care Visits	Relatedness	Fewer Symptoms
Hypertension/hyper-lipidemia/arthritis	17/21	0.20	0.61	0.56	0.56
Hypertension/hyper-lipidemia/diabetes	11/10	0.40	0.66	0.36	0.45
Hypertension/arthritis/diabetes	16/11	0.96	0.71	0.52	0.53
Hyperlipidemia/arthritis/diabetes	14/14	1.09	0.56	0.91	0.75

As mentioned above, C-CHESS will add to Elder Tree the Clinician Report (CR), which alerts clinicians when thresholds are reached in a patient's status. We used a similar system in a lung cancer RCT comparing CHESS to CHESS+CR. The addition of the CR to CHESS improved ($p < .001$) symptom distress by over 100% (26.2% improvement with CHESS vs. 53% in those with CHESS+CR; $n = 71$ vs. 68 respectively). These statistics are averaged across 6 observations over 12 months. We expect the proposed CR to increase the effects of C-CHESS compared with Elder Tree.

Innovation: The intervention is innovative for the following reasons.

1. *Single disease* \Rightarrow *Multiple diseases*. Information and communication technologies have shown promise in managing chronic conditions. But most address a single condition without addressing co-occurring issues. In contrast, C-CHESS will offer information for specific conditions as well as tools designed to improve behaviors that underlie MCCs generally, such as weight management. Patients will select behaviors they want to address. C-CHESS will be designed to help any combination of MCCs.
2. *Single intervention* \Rightarrow *Multiple interventions*.^{23,24} Many healthcare apps rely on one tool (e.g., texting), though different people with similar objectives may benefit from different tools. C-CHESS will offer a variety of options for online training and support.
3. *Complex* \Rightarrow *Simple*. Many computer-based systems make extensive use of text and are complicated to navigate. Additionally, systems on smartphones are often challenging for older adults because vision problems and tremors make it difficult to use the small keys. C-CHESS will improve ease of use by offering large screens, voice and text options, and simple content.
4. *Clinic-based and periodic* \Rightarrow *Sustained tracking and just-in-time clinician alerts*. Tracking and support for patients with MCCs usually consist of periodic, onsite contact with PCPs, who may be unaware of and/or cannot respond promptly to changes. Moreover, many patients avoid "bothering the doctor," foreclosing a source of help that might make a difference. C-CHESS will encourage patients to report symptoms daily, weekly, and monthly, depending on a patient's specific conditions and choice. When changes warrant just-in-time alerts, they will be automatically sent in a manner that minimizes clinician burden.
5. *C-CHESS will address loneliness*. Loneliness worsens chronic conditions. C-CHESS will address this by giving participants the power to give and receive social support.

The C-CHESS intervention

C-CHESS provides tools, motivation, and social support to help patients set, prioritize, track, and accomplish goals for managing their specific set of chronic conditions. C-CHESS is consistent with self-determination theory, which asserts that satisfying 3 fundamental psychological needs contributes to adaptive functioning: competence (feeling effective rather than overwhelmed), social relatedness (feeling connected to others), and feeling internally motivated (rather than coerced).⁴³

The following describes key C-CHESS behavioral services:

- Cognitive behavioral therapy (CBT) life skills summaries: Behavior change, problem solving, decision-making, managing stress and fatigue,⁴⁴ and resolving communication problems via skills such as cognitive reframing, analyzing your behavior chain, and attentive listening.
- Goal setting and reminders: Helps patients set behavioral goals and reminds them of treatment plan activities (e.g., exercise), upcoming appointments, events of interest, skills, online relaxation exercises, peer support, and distracting activities. Patients will be asked if they intend to meet certain self-determined goals because this has been shown to improve adherence.⁴⁵
- Treatment plan manager: Helps patients set priorities and reminds them to take medications and follow their treatment plan using schedules entered at setup and altered periodically as needed.
- Tracking, triage, and feedback: C-CHESS collects information about how a patient is feeling using patient-reported responses to prompts and provides links to relevant resources. Also sends inspirational messages and congratulations for patients' achieving their goals.
- Ask an Expert: Allows patients to anonymously seek advice about managing their MCCs.
- Tips and texts. Ideas on how to manage MCCs and their interactions.⁴² Patients and clinicians can add to or comment on tips, web links (e.g., AARP drug interaction checker⁴⁶), and other information.

Social engagement services provide:

- Social interaction options: Patients with MCCs give and receive support via emails, texts, and monitored online discussion groups. Past research consistently indicates that participating in social interaction via CHESS is associated with better health outcomes (e.g., quality of life, emotional well-being).^{47,48}
- Private messages: Enables C-CHESS members to communicate privately with other C-CHESS members. Along with discussion groups, private messages are one of the most popular services in current CHESS systems.
- Healthy Events: Suggests local activities that patients can add to their calendars according to guidelines established during setup.

C-CHESS's autonomy support tools provide:

- Thought for the Day provides motivational reminders of the importance of maintaining or improving health.
- Relaxation services: Games, recordings to guide progressive relaxation, deep breathing, and mindfulness.
- Personal stories: Audio/video accounts (based on interviews with MCC patients) focusing on care experiences (e.g., what patients would do differently, how they coped, tips they used).

C-CHESS Clinician Report (CR). MCCs can lead to rapid declines in health.⁸ The CR can share timely information on patient general indicators (e.g., fatigue, mood, nutrition, sleep). C-CHESS will help clinicians prepare for patient office visits.

1.0 STUDY OBJECTIVES

This project will test the use of an eHealth intervention called C-CHESS, to modify health behaviors and improve health outcomes in older adults with comorbid chronic diseases and health conditions.

Aim 1 Refine C-CHESS, using feedback from patients and primary care clinicians.

Aim 2 Conduct a randomized clinical trial to test 4 hypotheses:

1. *Primary outcomes:* Patients assigned to TAU+C-CHESS will have better quality of life and less primary care use (fewer visits) than those assigned to TAU+Internet.
2. *Secondary outcomes:* Patients assigned to TAU+C-CHESS will have improved composite scores; improved individual condition outcomes (mm Hg for hypertension, mg/dL for hyperlipidemia (LDL), HbA1c for diabetes, and pain for arthritis); and fewer symptoms from a list than patients assigned to TAU+Internet.
3. *Mediators:* Patients assigned to TAU+C-CHESS will have, compared with patients assigned to TAU+Internet, greater adherence to medications and appointments as well as improved competence,

relatedness, and autonomy.

4. *Moderators:* Improvements in primary outcomes for TAU+C-CHESS vs. TAU+Internet will be greater for women than men, those ≥ 75 vs. 65 to 74, and those with 3-5 chronic conditions vs. 6+.

Aim 3 Analyze data from the RCT and publish results.

Exploratory questions:

- Does C-CHESS reach a large proportion of targeted patients, get a large proportion of targeted clinicians to use C-CHESS, get a large proportion of patients to regularly use C-CHESS, and maintain that performance over time)?
- Does the use of specific C-CHESS services affect outcomes?
- Does the use of C-CHESS affect other health service use?

Primary Aim

Patients assigned to TAU+C-CHESS will have better quality of life and fewer primary care visits than those assigned to TAU+Internet.

C-CHESS will contain the Clinician Report to make it easier for PCPs to respond to important patient changes, pilot data suggested that primary care visits could be reduced. Reducing the number of primary care visits will both lessen provider burden and ultimately reduce healthcare costs.

Secondary Aim

Patients assigned to TAU+C-CHESS will have improved composite scores; improved individual condition outcomes (mm Hg for hypertension, mg/dL for hyperlipidemia (LDL), HbA1c for diabetes, and pain for arthritis); and fewer symptoms from a list than patients assigned to TAU+Internet.

A composite measure will combine Z scores of outcomes for each of the targeted chronic conditions, but because the composite score has not been validated and to help interpret results, we will also report results for each condition. Our pilot data showed positive effects for almost all combinations of conditions, and previous research (on breast³⁸ and lung⁴⁰ cancer; asthma³⁴; HIV³⁵; and alcoholism³⁹) has shown that CHESS programs improve outcomes for individual chronic conditions. In addition, an extensive review of mHealth apps for cardiovascular disease⁵⁹ found promising results of mHealth in RCTs on hypertension and hyperlipidemia. Few of the programs for diabetes have been rigorously tested and reported.⁶⁰ We chose pain as the outcome for arthritis because Internet-based interventions have proven effective in reducing pain.⁶⁴

Study Coordination

The UW-Madison Center for Health Enhancement Systems Studies (CHESS) is the coordinating site for this study. The UW study coordinator will oversee all recruitment activities which includes:

- developing recruitment and data collection processes that meet study objectives;
- training staff on protocol procedures prior to start of recruitment and continuous monitoring to assure compliance with the protocol and human subjects regulation;
- communicating with clinic site staff as needed via conference calls to monitor progress, inform of protocol changes/distribute new version of protocol, and address unanticipated issues or challenges;
- and manage all study data.

2.0 SELECTION OF SUBJECTS

Patient Recruitment: We will recruit 330 patients age ≥ 65 .

Patients are eligible for the study if they:

- 1) are ≥ 65 years old
- 2) have been treated in the clinic for at least the previous 18 months with no plans to leave during the study period

- 3) have ≥ 3 of the following chronic conditions:
 - Hypertension
 - Hyperlipidemia
 - Diabetes
 - Arthritis
 - BMI ≥ 30
 - Chronic Kidney disease
 - Chronic pain
 - COPD
 - Congestive heart failure
 - Arrhythmia/atrial fibrillation
- 4) report no current psychotic disorder that would prevent participation
- 5) have no acute medical problem requiring immediate hospitalization
- 6) do not have a visual or motor impairment that prevents them from using a computer
- 7) be able to read and sign the consent form in English
- 8) have no known terminal illness;
- 9) be willing to share health-related study data and
 - Systolic and diastolic BP
 - Weight
 - BMI
 - HDL/LDL
 - HbA1C
 - pain score
 - health care utilization: hospitalizations (admission and discharge), number of ER visits, urgent care visits, PC visits, specialty care visits, long-term care visits, and rehab visits
- 10) allow researchers to share information with their primary care physician

We will document and describe eligible people who choose not to participate.

Clinician Recruitment: 15 providers (salaried, credentialed staff) from 5 different clinic sites will be identified and recruited to complete 3 qualitative interviews each over the course of the study. Site staff will be identified by the clinic and contacted by the UW study coordinator. Details of the study and their participation will be explained and if they agree informed consent will be collected. Staff are eligible for the study if they:

- Allow monitoring of their C-CHESS usage
- Are willing to participate in 3 interviews to share information about technology use at their clinic and feedback related to C-CHESS.
- Have a patient participating in the intervention arm of this study

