3.0 REGISTRATION PROCEDURES

Patient Recruitment

In January of 2018, research staff will begin recruiting. The trial will involve 330 patients age 65 and older, randomized into two groups:

1. Patients in the experimental group will receive treatment as usual TAU + laptop + Internet access + C-CHESS
2. Patients in the control group will receive TAU + laptop + Internet access

Patient recruitment will be conducted in primary care clinics within the University of Wisconsin's Department of Family Medicine and General Internal Medicine, as well the Medical University of South Carolina.

School of Medicine and Public Health/MUSC employees will identify from clinic records patients who meet inclusion criteria.

The UW Clinical Research Data Service (CRDS) will extract the following data to determine patient eligibility per the eligibility criteria above. The data will be sent to the UW Office of Clinical Trials via REDCap or other secure method.

- First and last name
- Address
- Birth date
- Age
- UW Clinic Location
- Primary Care Doctor
- Has ≥ 3 of the following chronic conditions:
 - Hypertension
 - Hyperlipidemia
 - Diabetes
 - Arthritis
 - BMI ≥ 30
 - Chronic Kidney disease
 - Chronic pain
 - COPD
 - Congestive heart failure
 - Arrhythmia/atrial fibrillation
- # of chronic conditions
- Don't need an interpreter
- # of primary care visits in the last 18 months

Potential UW Health participants will either receive an opt-in letter from the UW Office of Clinical Trials or be recruited in-person at a scheduled clinic appointment. In the latter case, clinic staff or the Office of Clinical Trials will alert research staff when a potential participant has an upcoming clinic appointment. Staff will be available at the clinic on the specified date/time to conduct the enrollment visit if the patient agrees to speak with them.

Potential MUSC participants will receive an opt-in letter or MyChart message sent by the MUSC Biomedical Information Specialist. The message will describe the study and have a postage paid return letter inviting further contact from the UW study team.

Only MUSC, the UW Office of Clinical Trials, or SMPH Family Medicine staff will receive the list of potential subjects, process the mailings or MyChart messages, or identify upcoming clinic appointments.

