UW study staff will call potential participants who opt-in to provide a detailed study overview including the benefits and potential risks of participation. If the patient is interested in participating, they will be asked questions to determine final eligibility: 1) do they have any acute medical problem requiring immediate inpatient treatment, 2) are they willing to allow their health care provider to supply lab data to the study team, or 3) are they willing to allow the study team to share high level information (graph that charts weekly scores related to the quality of your sleeping, nutrition, physical activity, memory, falls, moods, balance, pain, medication adherence and quality time spent with others, 4) do they have any plans to change health care providers in the next 18 months.

Patients who verbally confirm they want to be in the study and meet the screening criteria will be mailed the baseline survey and will receive a home visit where written consent will be obtained, the completed baseline collected, randomization determined, equipment set up, and training delivered. The baseline survey is expected to take 20-30 minutes to complete and will assess demographics, quality of life, symptom management, pain, medication adherence, and health care utilization.

Patients who consent to participate in-person at a clinic appointment will provide signed consent, be given the baseline survey, and a home visit will be scheduled to complete the activities described above.

Minority Recruitment Advisors

In addition to the general recruitment procedures described above, beginning in October 2019 three individuals active in the black community in Madison, WI will serve as advisors to the research team. They will provide feedback on recruitment materials, recruitment process, and ElderTree content and design which will inform future projects.

Patient Consent

Patients must agree to allow monitoring of their C-CHESS use and agree to allow their clinic to supply the study team with health care utilization and EHR related data, specifically lab scores for systolic and diastolic BP, weight, BMI, HDL/LDL, HbA1C, and pain. (as applicable to the patient), and diagnoses of anxiety, depression, osteoporosis, and cancer. The patient will be given the right not to share specific information and will retain the right to revoke their permission at any point.

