Participants who do not already own a computer will be receiving a laptop as part of the study. The laptop has an administration interface that allows our technical team to access devices remotely if a participant calls tech support or reports a problem. If a participant loses their laptop or installs something that is causing problems, we have the ability to remotely wipe the device, lock it down, restore the operating system and/or run a security check. We can also do security updates remotely to make sure patches are up to date on each laptop and security software has not been disabled by the user.

Patient Randomization: Once informed consent and baseline measures have been obtained from patients, they will be randomized to either the experimental (TAU + C-CHESS) or control (TAU + Internet) group, stratified on gender, clinic site, and number of chronic conditions (3-5 vs. 6+). Patients who are in the experimental group will be further randomized into two groups, one will be asked to identify a health outcome to track and share with their physician using the Clinician Report and the other group will not.

When baseline assessment and consent are complete, the researcher will enter the participant number and randomization data into a randomization spreadsheet. The interviewing researcher, once informed of group assignment, will provide setup and training.

The research staff will train participants to use C-CHESS and customize it (e.g. by health condition) during a home visit. Participants will be asked to check in regularly, initially at a daily rate with frequency of at least weekly over the course of the study.

Patient Qualitative: Data will be gathered via an interview at 3 times from 6 patients at each of the 5 clinics (N=30). Each interview is expected to take 30-60 minutes and will take place either in-person at a place of the subjects choosing or via phone.

Recruitment: Participants will be identified through a consent form opt-in question and demographics as reported on the baseline survey. We will seek a mix of genders and number of chronic conditions. We will also look at C-CHESS use data to find a mix of users and non-users. We will contact potential participants by messaging them through the C-CHESS application or phoning them.

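### Screening does not ask about earlier Elder Tree use or a participant in the same home, so some controls could be partly exposed; the gap is cheap to close

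*Combined protocol and SAP*

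**What the plan says.** The opening description of the intervention introduces the product as "C-CHESS (or ElderTree, as it will be known to participants". Under Preliminary data the protocol says that "C-CHESS will have as its base the services and design of Elder Tree", with condition-specific features and the Clinician Report added. The same section reports that "Elder Tree was tested in an RCT involving 399 older adults from 3 Wisconsin counties", followed for 18 months, and adds: "We identified 66 older adults with at least 3 of the 4 target MCCs". That count covers both arms of the earlier trial.

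On recruitment, section 3.0 states: "Patient recruitment will be conducted in primary care clinics within the University of Wisconsin's Department of Family Medicine and General Internal Medicine". The Medical University of South Carolina (MUSC) clinics are the other source.

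Section 2.0 lists ten patient criteria. The one on clinic history requires that patients "have been treated in the clinic for at least the previous 18 months with no plans to leave during the study period". In section 3.0, patients who opt in are telephoned, and "they will be asked questions to determine final eligibility". There are four questions: acute illness, release of lab data, sharing of weekly scores, and plans to change provider. Patients approached at a clinic appointment sign consent there and are then booked for a home visit; the four questions are not described for that route.

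Randomisation is by individual patient, "stratified on gender, clinic site, and number of chronic conditions (3-5 vs. 6" or more). Setup and training take place at the home visit, and each C-CHESS user has a personal login.

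**The concern.** C-CHESS shares its base, its name and its developer with a system already tested in older adults in one of the two recruiting states. The protocol uses the earlier trial's effect sizes in its own power analysis, so it regards Elder Tree as active. A former Elder Tree user allocated to control has already had part of what the trial is testing, and one allocated to C-CHESS may have less left to gain.

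The household route is separate. Two people aged 65 or over in one home can both qualify, and under independent 1:1 allocation they end up in different arms about half the time. The control partner then lives where C-CHESS has been installed and taught. Use is logged by account, so a control who uses a partner's login would appear in the logs as the partner.

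Both routes would shrink the quality-of-life and primary-care-visit differences. If neither fact is recorded, the extent cannot be assessed afterwards.

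**Working it through.** **1. The plan's own figures (section 8.0).** Inputs: d = .40, power .80, two-sided alpha .05.

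n per arm = 2(1.960 + 0.842)² / 0.40² = 2 × 7.849 / 0.16 = 98.1, so 99, against the stated 100. Attrition: 264 / (1 − 0.20) = 330, exact. The step from 100 to 132 per arm has no stated formula and was not reproduced; nothing below depends on how it was derived.

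**2. Where the two facts could have been caught.**

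| Place | Earlier Elder Tree use | Co-resident participant |
|---|---|---|
| Ten criteria (2.0) | no | no |
| Record extract (3.0) | no | address extracted, no check described |
| Phone screen (3.0) | no | no |
| Strata (3.0, 7.0) | no | no |
| Model terms (6.0) | no | no |

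**3. Illustrative dilution.** Let c be the share of controls who receive the full effect. The observed difference is d(c) = 0.40(1 − c). The same formula applies if a share c of both arms are earlier users among whom the arms do not differ. Power at 132 per arm = Φ(d(c) × √(132/2) − 1.960), with √66 = 8.124.

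| c (assumed) | d(c) | Power at 132 per arm |
|---|---|---|
| 0% | .400 | .901 |
| 2% | .392 | .890 |
| 5% | .380 | .870 |
| 10% | .360 | .833 |
| 15% | .340 | .789 |
| 20% | .320 | .739 |

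The t distribution gives .899, .868 and .830 at 0%, 5% and 10%.

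**4. Where power reaches .80.** d = (1.960 + 0.842) × √(2/132) = 0.345, so c = 1 − 0.345/0.40 = 0.138, about 14%.

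**5. What such a c would require.** The documents give no rate, so these figures show scale only.

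- Households: if a fraction q of participants enrol with a partner, about q/2 of controls have a C-CHESS partner. For c of 5% to 10% by this route alone, q must be 10% to 20%; for 14%, about 28%. In every case each such control would have to gain the full effect.
- Prior use: if half of the 66 were on Elder Tree (an assumption), that is 33 people, and 33/330 = 10%. Split 1:1, 16.5/165 = 10% of controls. This needs every one of them to attend a recruiting clinic and enrol. It is not a ceiling either, because the 66 were counted on four conditions and section 2.0 now admits ten.

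**6. Smaller analyses.** Condition-specific outcomes use only patients with the diagnosis. With 100 per arm (the plan's base figure, not a stated size for any condition), power at c = 0%, 5% and 10% is .807, .766 and .721.

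**The case against.** Exposure is possible but not shown. The documents do not say that the three pilot counties overlap the recruiting clinics or that earlier users kept access, and nothing points to prior exposure from that trial at the South Carolina clinics. Elder Tree is also only the base of C-CHESS, without the added condition content or the Clinician Report. All of this stands. A reader might infer that controls already have the intervention; the documents support only that some could have had its base.

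A reader might also infer that prior use corrupts the baseline of C-CHESS patients in particular. It does not. Baseline is measured before randomisation, earlier users fall in both arms, and the baseline value is a covariate. The comparison remains valid; the incremental effect may simply be smaller in that subgroup.

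Household sharing is limited. The protocol assumes about half of participants own a computer, and only those without one receive a laptop, so a study laptop will often not be present. Access needs a personal login, content is customised to the user, and a partner cannot obtain their own check-ins or Clinician Report through another person's account. Full transfer is therefore a worst case for each exposed control. These barriers reduce sharing but do not exclude it; a couple may share their own computer. Stratifying by gender is not the cause, since individual 1:1 allocation splits about half of couples in any case.

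Finally, excluding couples loses eligible patients for a gain that cannot be quantified. That is fair, and it is why this is offered as an improvement and not as a defect that must be repaired.

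**Conclusion.** The omission is confirmed in the criteria, the record extract, the phone screen, the strata and the model. Its consequence is possible dilution of both primary differences toward zero, of unknown and probably modest size. In the illustration, 5% to 10% of controls with the full effect reduces d from .40 to .38 to .36 and power at 132 per arm from about .90 to .87 to .83, still above the planned .80. Power falls below .80 only above about 14%.

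This rests on an assumed exposure rate, full effect in each exposed control, 132 evaluable patients per arm, and no allowance for correlation between partners. A reader might infer from the gap that the trial is underpowered or its comparison invalid. The documents support neither: they give no rate of prior use or cohabitation, and the planned sample has some reserve. What they support is a cheap improvement.

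**What to change.** For patients not yet enrolled, add two criteria to section 2.0:

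- No earlier use of Elder Tree, established by one screening question and, where the centre still holds it, a check against the earlier trial's participant list.
- One randomised participant per household, checked by address. The University of Wisconsin extract already contains it; for MUSC the address can be checked when the home visit is booked.

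Apply both to the telephone route and to in-clinic enrolment, because the phone questions as described would miss patients enrolled at an appointment.

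Recruitment was planned from January 2018 and the text also refers to October 2019, so some patients may already be enrolled. For them, record earlier Elder Tree use and co-residence with another participant, and repeat the primary analysis without those affected as a sensitivity analysis.

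The cost is two criteria, two questions, a list check if the list survives, and the loss of a small number of otherwise eligible patients, mainly couples.
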